following urinary symptoms is required for UTI diagnosis in patients using intermittent catheterization: new onset or worsening fever, rigors, altered mental status, malaise, lethargy with no other identified cause, flank pain, costovertebral angle tenderness, acute hematuria, pelvic discomfort, increased spasticity, autonomic dysreflexia or sense of unease. The Guidelines specifically state that “the presence or absence of odorous or cloudy urine should NOT be used as an indication for urine culture or antimicrobial therapy” and “the presence, absence or degree of pyuria should NOT be interpreted as an indication for antimicrobial treatment.” If a subject presents with any of these symptoms and there are $\geq 10^3$ cfu/hpf bacterial growth on urine culture, the subject will be excluded and treated for a UTI according to clinical best practice.

Participant Burden:

Urine samples for urinalysis, urine culture and metagenomic sequencing will be obtained at up to monthly for the first year of study participation when not experiencing symptoms, at up to 2 occurrences of urinary symptoms during SMP_{PRO} intervention phase, and follow-up after either lactobacillus treatment or antibiotics and at follow-up, for a total of up to 18 samples per patient depending on the frequency with which urinary symptoms are experienced. When possible, our Research Assistant will meet with the patient at a mutually convenient location.

Baseline Data Collection:

Per IRB protocol # 2014-211 phase II, after consent, participants will complete the Health History Questionnaire, Urinary Symptom Questionnaire, In addition to questionnaires, all participants will provide a urine sample using sterile catheterization techniques. Thereafter, participants will complete the Urinary Symptom Questionnaire weekly.

Intervention:

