After 6 months of baseline data collection the intervention phase will begin. Prior to implementing the intervention protocol, participants will provide study staff with a urine sample either at MedStar NRH, CNMC, or when possible, the study RA will meet with the participant at a mutually convenient location. After urine sample is collected, study participants will follow the study protocol and complete USQ-NB weekly. If/when urinary symptoms occur, they will be instructed to follow the SMP_{PRO} protocol to determine whether to initiate intravesicular *Lactobacillus* instillation or be evaluated by a physician. The self-management protocol (SMP_{PRO}) will also direct them to discontinue *Lactobacillus* instillation or be evaluated by a physician if symptoms remit, persist or worsen. If participants are directed by the self-management protocol to seek medical attention or s/he feels the need for medical evaluation, s/he will be advised to obtain care as they typically would by their health care provider. Participants will be supplied with letters to be brought to their health care provider notifying them of the study and requesting sharing of urinalysis and urine culture results with the research team. A verified UTI will include those that resulted in antibiotic treatment by a health care professional. An additional urine sample for metagenomics will either be left with the health care provider for pick up by the research team, brought to the research site, or obtained by the RA at a mutually convenient site. If participant is treating urinary symptoms at home with *Lactobacillus*, a urine sample will be dropped off either at MedStar NRH, CNMC or when possible, the study RA will meet with the participant at a mutually convenient location.

The Impact of Self-Management with Probiotics on Urinary Symptoms and the Urine Microbiome in Individuals with Spinal Cord Injury and Spina Bifida Protocol

5/18/2017

Page 8 of 17

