For the intravesicular *Lactobacillus* instillation, the contents of 1 *Lactobacillus* capsule will be mixed into 45 cc sterile 0.9% saline (adult bladder volume is 450cc, so this amount represents 10% of adult bladder volume). After mixing, study personnel will draw up the 45 cc of the liquid *Lactobacillus* mixture into a 60cc catheter tip syringe and instill via the intermittent catheter. For children volume is based on age (see table on page 4 of protocol). Study participant will recheck symptoms after 24 hrs (valid range 22-30 hrs) following the SMP_{PRO} protocol and either complete another *Lactobacillus* instillation or seek medical attention. If symptoms still persist 4 hrs after second instillation, study participants should seek medical attention.

Post-Intervention Follow-Up:

After completion of the 6-month patient-initiated self-management protocol intervention period, participants will monitor symptoms weekly using the USQ-NB. At the end of follow-up, we will obtain another urine sample from all participants.

Measurements:

In addition to the measurements described in Phase II the following measurements will occur for phase III;

Urine Acquisition: A 50-100 ml urine sample will be collected from each subject for (1) urinalysis and cultivation, and (2) urine microbiome by SMRT sequencing. Urine will be collected from a new, unused intermittent catheter.

Urine Preparation: Collected urine will be immediately placed at 4°C. Within 6 hours, samples will be taken to CNMC for sequencing preparation. At CNMC, urine samples will be centrifuged at 4°C, 5,000 x g for 20 minutes. The supernatant will be aliquoted in 2 ml cryotubes and frozen at -20°C. 10ml PBS will be added to the pellet with the remaining supernatant and then centrifuged (5,000xg) at 4°C for 20 minutes. The pellets and aspirated PBS wash solution will be stored at -20°C. Pellets will later be transferred for DNA isolation and SMRT sequencing.

Urinalysis: Urine samples will be assessed utilizing standard clinical microbiology semiquantitative chemical testing using commercial disposable test strips for glucose, bilirubin, ketone, specific gravity, blood pH, protein, urobilinogen, nitrite, and leukocyte esterase. After centrifuging for 5 minutes, microscopic examination for and quantification of WBCs, RBCs, epithelial cells, yeast, bacteria, *Trichomonas vaginalis*, sperm cells, mucous filaments and crystals will be performed using standard microbial techniques.

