To determine whether bacterial diversity differs between study groups the Shannon Diversity Index will be used. The Shannon Index is a measure of sample diversity that takes into account total number of bacterial types in the sample and relative proportion of the bacterial types. From the subsample of 50 participants giving urine samples, subjects who did in fact utilize the SMP at least once during the 6-month SMP time frame will be stratified into two groups, those who responded to SMP and those who did not; we will define "response" as the observation of a 10% or more decrease in the average number of USQ items endorsed within any time frame, so that each of the 50 persons in this sub-sample will be characterized as either a responder (10% or more decrease) or a non-responder (0-9.99% decrease). A scatter plot of response group versus Shannon Index will be produced, and a mixed effects linear regression model will test the individual (main) and interaction effects of response group and time on Shannon Index. A positive time coefficient is indicative of increased microbiome diversity and a negative time coefficient indicates reduces diversity. The magnitude of difference between the response groups will be determined using the Yue-Clayton theta similarity index (θ). The θ index measures the difference in the number and relative abundance of bacterial species between samples^{4,5} when $\theta=1$ two samples have identical community structure and when $\theta=0$ indicates complete dissimilarity between samples. Pathoscope will be used to calculate abundance of different taxonomic groups at each time point.

REFERENCES

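### H4 compares urinary diversity by response group and time without accounting for antibiotic exposure, so a responder difference can partly reflect antibiotic use, of unknown size and direction

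*Combined protocol and SAP*

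**What the plan says.** All references are to the combined protocol and SAP.

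- **H4, model.** The plan is that "a mixed effects linear regression model will test the individual (main) and interaction effects of response group and time on Shannon Index". No other term is named. H4 does not say which samples enter or how time is coded.
- **H4, analysis set.** The text reads "subjects who did in fact utilize the SMP at least once during the 6-month SMP time frame will be stratified into two groups". Nobody is excluded or separated because of antibiotic use.
- **H4, response.** Response is "the observation of a 10% or more decrease in the average number of USQ items endorsed within any time frame". The definition does not depend on which treatment produced the decrease.
- **Phase III, Participant Burden.** The sampling list includes "follow-up after either lactobacillus treatment or antibiotics and at follow-up, for a total of up to 18 samples per patient".
- **Phase III, Intervention.** When a participant goes to a provider, a sequencing sample is also taken: "An additional urine sample for metagenomics will either be left with the health care provider for pick up by the research team". On persistent symptoms: "If symptoms still persist 4 hrs after second instillation, study participants should seek medical attention". On infection: "A verified UTI will include those that resulted in antibiotic treatment by a health care professional".
- **H3.** Antibiotic use is collected as a count per patient, from records or self-report, and serves as the H3 outcome. No course dates are specified.

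**The concern.** Three features of the plan combine. Sequenced urine can follow an antibiotic course. The groups being compared are defined by symptom course. Symptom course also influences who goes to a provider, where antibiotics may be prescribed. Antibiotic exposure can therefore differ between responders and non-responders, and the model has no way to separate that from anything Lactobacillus does to the microbiome.

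The time factor raises a related question of interpretation. H3 expects fewer antibiotic courses under self-management, so the plan itself anticipates that exposure will change between periods. A change in diversity over time could be read as a direct action of the instilled bacteria when part of it comes from fewer antibiotics.

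What is at stake is the microbiome conclusion, which is a secondary outcome of a pilot. The primary outcomes are not touched.

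**Working it through.** **No plan figure to reproduce.** H4 states no sample size justification, effect size, SD or alpha. The check is a reading of the text, followed by an illustration of scale.

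**1. Does anything elsewhere close the gap?**

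- The two-week antibiotic exclusion in the Phase III criteria applies to candidates at entry. It does not govern samples during the following 18 months.
- The allowance for covariates in the analysis text belongs to the H1 models for symptoms and UTIs. It concerns gender, age and sex. Antibiotics are not named, and H4 does not repeat it.
- Each participant being his or her own control does not help, because antibiotic exposure varies within a person over time.

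**2. Size of a spurious group difference.** Let D be the amount by which recent antibiotic use lowers the Shannon Index, and let p_R and p_N be the proportions exposed among responders and non-responders. With no Lactobacillus effect, the expected difference in change (responder minus non-responder) is

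difference = D × (p_N − p_R).

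None of these inputs is in the documents. Taking D = 1 SD as an assumption:

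- p_R = 20%, p_N = 50%: 1 × (0.50 − 0.20) = 0.30 SD
- p_R = 20%, p_N = 80%: 1 × (0.80 − 0.20) = 0.60 SD
- p_R = p_N = 30%: 1 × (0.30 − 0.30) = 0
- p_R = 50%, p_N = 20%: 1 × (0.20 − 0.50) = −0.30 SD, so the sign reverses

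**3. How often would this be declared significant?** A simulation of the group-by-time contrast used the following further assumptions: one pre and one post value, two equal groups, within-person correlation 0.5, two-sided alpha 0.05. The subsample is given as 20 in H2, 30 in the Phase III design and 50 in H4, so all three were run. Results for D = 1 SD:

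| N | Exposure, R vs N | Rejection, planned terms only | Rejection, antibiotic term added |
|---|---|---|---|
| 20 | 20% vs 50% | 9.0% | 4.9% |
| 20 | 20% vs 80% | 23.3% | 5.2% |
| 30 | 20% vs 50% | 12.0% | 4.8% |
| 30 | 20% vs 80% | 32.5% | 5.2% |
| 50 | 20% vs 50% | 15.6% | 5.6% |
| 50 | 20% vs 80% | 49.2% | 4.7% |

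Over D from 0.5 to 1.5 SD with these unequal splits, the spurious difference runs from 0.15 to 0.90 SD. Rejection runs from 6.7% to 38% at N = 20, 6.6% to 55% at N = 30 and 8.2% to 76% at N = 50. With the antibiotic term it is 4.6% to 6.0%. With equal exposure, rejection is about 5% without any adjustment. The adjusted model does this well partly because the simulation makes it the correct model.

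**4. How common might recent exposure be?** For a sample taken at a random time, with r treated UTIs per 182.5 days, the share within w days of a course start is 1 − exp(−r × w / 182.5).

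| r per 6 months | Source | w = 30 days | w = 14 days |
|---|---|---|---|
| 1 | Eligibility minimum of 2 UTIs a year | 15% | 7% |
| 4.75 | Power calculation, detectable value | 54% | 31% |
| 6 | Power calculation, hypothetical baseline | 63% | 37% |

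The 30-day share therefore ranges from about 15% to 63%, depending on the rate assumed. This shows only that exposure need not be rare. It says nothing about how exposure divides between response groups. The routine monthly samples are taken in symptom-free periods, so they are not randomly timed. Post-treatment samples follow treatment by design, so the formula does not describe them.

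**The case against.** The strongest reply is that H4 tests a strategy, not a product. Self-management includes going to a provider when needed, and fewer antibiotic courses is one of its hypothesised benefits (H3). Antibiotic use then lies on the pathway from strategy to microbiome, and adjusting for it removes part of the effect being estimated. For the comparison between periods this stands. A reader might infer that H4 cannot answer its own question as modelled. The documents do not support that, because the unadjusted time effect is a legitimate total effect.

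Three other stronger readings also fail.

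- **That H4 pools post-Lactobacillus and post-antibiotic urine.** H4 never defines its sample set. It could use only a few fixed points, as H2 does for white cell counts and H3 does with its three periods. The textual defect is the missing definition. Recent antibiotics could still affect samples at fixed points.
- **That non-responders are the ones who had antibiotics.** The referral route makes this plausible, but a participant whose symptoms fell after antibiotics counts as a responder. The documents give no antibiotic use by group.
- **That 63% versus 54% of samples would follow antibiotics.** Those figures rest on hypothetical power inputs, and they compare periods, not response groups. At the eligibility minimum of about 1 UTI per 6 months, with the same proportional reduction (4.75/6), they become 15% versus 12%.

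It is also fair to say that adjustment is no full cure. Both response and antibiotic use arise after baseline.

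**Conclusion.** The concern holds in a limited form. H4 takes no account of antibiotic exposure, and nothing elsewhere in the document does so for it. A responder versus non-responder difference in Shannon Index, or a group-by-time interaction, can therefore partly reflect antibiotic use. Size and direction cannot be known from the documents, and the bias is zero if exposure is equal. The 0.30 to 0.60 SD illustration depends wholly on an assumed 1 SD antibiotic effect and assumed exposure splits. The time effect may stand as the total effect of the strategy, provided it is not reported as a direct Lactobacillus effect. The matter is worth correcting because the fix is cheap, but its reach is confined to a secondary outcome of a pilot that sets out to estimate associations.

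**What to change.** 1. State in H4 which of the up to 18 samples enter the Shannon model and how time is coded. Reconcile the subsample size (20, 30 or 50) at the same time.
2. Record the dates of each antibiotic course so that they can be set against sample dates. The H3 count alone does not place exposure before or after a given sample.
3. Keep the planned model. Beside it, report a sensitivity analysis that either adds a time-varying term for antibiotic exposure (for example any course in the previous 30 days) or leaves out post-antibiotic samples.
4. Report post-treatment samples separately for episodes treated with Lactobacillus only and episodes treated with antibiotics.
5. Say in the interpretation that the unadjusted time effect is the total effect of the strategy, including any antibiotic sparing.

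The cost is SAP wording, some date capture that may be hard to recover later, and one or two extra parameters in a small subsample. The responder comparison remains associational after these changes.

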If participants instill *Lactobacillus* at any time during the intervention phase, and after *Lactobacillus* instillation reports a UTI as an Adverse Event (AE) we will request their urinalysis and urine culture results to attempt to determine if *Lactobacillus* might have been the cause of the UTI. If determined necessary by the PI, Co-PI and/or DSMB other AEs reported could require retrieval of medical records.

Phase III: Pilot Study of Multiple (up to 2) *Lactobacillus* Bladder Instillations

We will recruit 30 persons in whom we will collect urine up to 18 timepoints (up to monthly for the first year when not experiencing symptoms, up to two times when subject experience urinary symptoms, follow-up after either *Lactobacillus* treatment or antibiotics, and three (3) months into the six (6) months follow-up) in order to **estimate the strength of the associations between successful implementation of the probiotic self-management program and urinary symptoms, bladder inflammation, and the urine microbiome.** We will conduct an 18-month study in which each participant will serve as his/her own control through 3 phases of study: 6-months usual care (baseline), 6-months probiotic intervention, and 6-months follow-up
Study Design: We will recruit N=30 subjects with neuropathic bladder who will contribute urine samples for analyses.

Clinical Setting: MedStar National Rehabilitation Hospital and Children's National Medical Center.

Target Enrollment: 30 adult subjects at least 1-year post-injury and 18 years of age with SCI/MS or at least 18 years of age with SB

Recruitment Strategy: SCI/MS and SB subjects will be enrolled with assistance from United Spinal Association. Additionally, we will query the MedStar National Rehabilitation Hospital inpatient service, the 40+ MedStar National Rehabilitation Network outpatient sites, various MedStar Network databases, and the CNMC Spina Bifida database. Databases will be queried for participants who meet the eligibility criteria and have already provided HIPAA authorization and consent to be contacted for future research. Announcements and IRB-approved flyers will be posted on the United Spinal Association and study websites and at participating institutions.

Informed Consent: Consent will be obtained by the PI, Study Coordinator, or Research Assistant. All project staff are currently CITI certified and have passed all requirements for HIPAA certifications.

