H4. Compared with usual management, self-management of urinary symptoms with probiotics will return the microbiome to baseline (Secondary outcome). For analysis of the microbiome, the fasta and fastq files of each sample's CCS reads will be retrieved and processed using LUCY⁵⁴ to filter out reads with low quality segments, as well as remove sequences that are shorter than the full length 16S rRNA (approximately 1500 bp). The sequences will then be aligned against the SILVA 16S rRNA database followed by subsequent implementation of Mothur's Chimera Slayer to filter out chimeric reads from sequences in each sample. The remaining sequences will undergo taxonomic classification. Bowtie2 will align each sequence read to a reference genome derived from the SILVA 16S database and output a SAM file. With the resulting SAM file, Pathoscope⁵¹ is capable of characterizing the biological sample to the subspecies-level, generating an excel file with the proportions of each classified organism within the sample tabled.

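### H4 asks about self-management against usual care, but its analysis is built around responders versus non-responders, and the one model term that could answer H4 is neither named as its test nor fully defined

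*Combined protocol and SAP*

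**What the plan says.** The H4 paragraph states the hypothesis as: "Compared with usual management, self-management of urinary symptoms with probiotics will return the microbiome to baseline". The Phase III section supplies the comparator. There is no concurrent control, and "each participant will serve as his/her own control through 3 phases of study: 6-months usual care (baseline), 6-months probiotic intervention, and 6-months follow-up".

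The diversity analysis under H4 opens with a different question: "To determine whether bacterial diversity differs between study groups the Shannon Diversity Index will be used". The groups are then defined. Among those giving urine, "subjects who did in fact utilize the SMP at least once during the 6-month SMP time frame will be stratified into two groups", responders and non-responders. Response is "a 10% or more decrease in the average number of USQ items endorsed within any time frame", and non-response is a decrease of 0 to 9.99%.

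The plan says that "a mixed effects linear regression model will test the individual (main) and interaction effects of response group and time on Shannon Index", and then interprets one of these terms: "A positive time coefficient is indicative of increased microbiome diversity and a negative time coefficient indicates reduces diversity". The Yue-Clayton index is used for the size of the difference between the response groups.

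No alpha, effect size, SD or power is given for H4.

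**The concern.** The hypothesis concerns one period against another within the same people. The analysis is organised around two kinds of SMP user. A group main effect says whether responders and non-responders differ in diversity overall. The interaction says whether they change differently. The Yue-Clayton index says how far their communities differ. None of these compares the SMP with usual care.

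Two wrong conclusions become possible. If the SMP shifts diversity equally in all users, the responder comparisons have nothing to find, and a reader who takes them as the H4 result would call H4 unsupported. If diversity merely tracks symptoms, those comparisons could be significant although the SMP did nothing, and that could be reported as support. The second risk is a matter of reasoning; it was not quantified.

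The time term is the natural place for the H4 answer, but the plan leaves open whether it is an average over both groups or the change in one reference group. With an interaction in the model these are different quantities.

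**Working it through.** **Comparing the hypotheses.** The H2 and H3 paragraphs make time the factor of interest and state a comparison with the pre-treatment period. The H4 paragraph has no such sentence and defines no contrast for a return to baseline.

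**Who is in the model.** Three points follow from the H4 text:

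- Only SMP users are stratified.
- The split rests on an outcome observed after baseline.
- A user whose symptoms increase has neither a decrease of 10% or more nor one of 0 to 9.99%, so has no group.

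**Power.** The plan has no H4 figure to reproduce; its only power figure, 81%, concerns the two H1 outcomes. The following comparison therefore rests on assumptions.

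Inputs:

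- N = 30, the Phase III recruitment target. (The H4 paragraph says 50 and the H2 paragraph 20.)
- Two-sided alpha 0.05: assumed. The 0.025 in the power section is set for the two primary outcomes.
- Mean SMP-minus-usual-care change in Shannon Index of 0.5 SD of the within-person change, the same in everyone: assumed.
- All 30 used the SMP and can be classified, response is unrelated to diversity, and variances are equal: assumed.
- Share of responders 60%, 80% or 90%: assumed. This gives 18/12, 24/6 or 27/3 responders/non-responders.

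Each power comes from the noncentral t distribution with noncentrality δ.

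1. Period contrast in all 30: δ = 0.5 × √30 = 2.739 with 29 df. Power is about 75%.
2. Time effect averaged equally over groups: SE = 0.5 × √(1/n_R + 1/n_N), δ = 0.5/SE, 28 df.
3. Time coefficient as the change in a reference group of size n: δ = 0.5 × √n, 28 df with pooled variance.
4. Group-by-time interaction: both groups change equally, so δ = 0 and the test rejects at its alpha, 5% here.

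| Responders / non-responders | Equal-weight SE | Equal-weight δ | Equal-weight power | Non-responder reference: δ, power | Responder reference: δ, power |
|---|---|---|---|---|---|
| 18 / 12 | 0.186 | 2.683 | 74% | 1.732, 39% | 2.121, 54% |
| 24 / 6 | 0.228 | 2.191 | 56% | 1.225, 22% | 2.449, 66% |
| 27 / 3 | 0.304 | 1.643 | 36% | 0.866, 13% | 2.598, 71% |

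The equal-weight figure falls with imbalance because the smaller group receives half the weight: at 24/6, six people carry as much as the other 24.

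**Cross-check.** The three-period model with a random subject intercept was simulated with 30 users, 50% or 70% responders, and a shared shift of 0.5 to 1.0 times the SD of a single measurement within a person (a different scale from the SD of change above). The time main effect (2 df) was detected in 42% to 98% of runs and the non-responders' SMP-versus-baseline change in 18% to 76%. Over 20, 30 and 50 users, the interaction test rejected in 4.3% to 5.5%.

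**The case against.** A reader might infer that the plan has only about 5% power for H4, or would necessarily miss an effect shared by all users. The documents do not support that. The model explicitly tests main effects, time among them, and the plan interprets the sign of the time coefficient. In an own-control design, time is the within-person comparison with usual care. If main effect has its ordinary meaning, an average over groups, the loss against a contrast in all participants is negligible when the groups are near balance (74% against 75%). The 5% is the interaction test's type I error under a true null, at an alpha the plan does not state for H4. It is not the power of the plan.

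The responder analysis also has a purpose. Phase III aims to estimate associations between successful use of the programme and the microbiome, and people who never had symptoms may never have instilled anything. Restricting to users is therefore a choice of estimand (use rather than offer), not an error in itself.

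Finally, a period contrast does not test H4 as worded either. A difference in diversity from the usual-care period is not evidence of a return to baseline.

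All of this stands. It does not settle which term decides H4, how time is coded, or where users who worsen belong. The 22% to 66% spread at 80% responders comes from the coding alone.

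**Conclusion.** The concern holds in limited form. The group effect, the interaction and the Yue-Clayton index do not address H4, and by construction they are blind to a change shared by responders and non-responders. The time main effect can detect such a change. However, it is not designated as the H4 test, its coding is unstated, and it is estimated only in SMP users divided on a post-baseline outcome that leaves those who worsen unclassified.

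Under the stated assumptions, a period contrast in all 30 has about 75% power. The planned time term ranges from nearly the same (74%) to 36% if averaged equally over groups, and is 22% or 66% at 80% responders if it belongs to one reference group. These figures depend on the assumed effect, alpha, sample size and response share. The mismatch between hypothesis and analysis does not. H4 is a secondary outcome in a pilot, so this is a correction worth making rather than a threat to the trial's main conclusions.

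**What to change.** Bring H4 into line with H2 and H3:

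- Fit a mixed model of Shannon Index on period (usual care, SMP, follow-up) with a random subject intercept, in all Phase III participants with urine samples and without a response-group term.
- Report the SMP-minus-usual-care and follow-up-minus-usual-care contrasts with confidence intervals as the H4 analysis. Give the same contrasts in SMP users as a supporting analysis.
- Describe the result as change in diversity from the usual-care period, not as a test of return to baseline.
- Label the responder main effect, the interaction and the Yue-Clayton comparison exploratory. State the coding of time, and assign users whose symptoms worsen to a group.

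The cost is revised wording and contrasts from samples already planned. There are two downsides: the responder comparison loses its standing as a test of H4, and including people who never used the SMP may dilute the effect, which is why the analysis in users is kept alongside.
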